4.1 Device description

Cochlear implant sound processors to be used in this study may include commercially available Nucleus sound processor systems.

4.2 Programming Software Description

4.2.1 Custom Sound 5.1

Programming of the sound processor is achieved via the commercially available and FDA approved Cochlear Nucleus Custom Sound (CS) software. In addition, the psychoacoustic tests will be used to assess performance of the subject and provide

the audiologist with programming parameter suggestions. Each clinical site will be provided a laptop which includes software to complete psychoacoustic testing, advice provided through Artificial Intelligence in addition to CS for use in the study.

4.3 Subject Population

Study sites will enroll up to 50 adult cochlear implant candidates at up to 5 North American cochlear implant centers.

Subjects must meet the following inclusion and exclusion criteria (Group A and B):

4.3.1 Inclusion Criteria

1. Patients who are receiving a commercially available Nucleus® electrode
2. 18 years and older
3. Postlingual onset of hearing loss (onset of hearing loss >2 years of age)
4. Individuals who qualify for cochlear implantation using the clinics current CI candidacy criteria
5. Individuals who have recently been implanted but not yet had their external device activated
6. Willingness to participate in a study and comply with all study requirements
7. Fluent in spoken English

4.4 Exclusion Criteria

1. Ossification or any other cochlear anomaly that might prevent insertion of less than 10 electrodes of the electrode array
2. Diagnosis of retro-cochlear pathology
3. Diagnosis of auditory neuropathy
4. Acoustic component in the implanted ear
5. Severe-profound sensorineural hearing loss >30 years
6. Previous cochlear implantation in either ear
7. Unrealistic expectations on the part of the subject regarding the possible benefits, risks, and limitations that are inherent to the surgical procedure and use of the prosthetic device

8. Unwillingness or inability to comply with all investigational requirements
9. Additional cognitive, medical or social handicaps that would prevent completion of all study requirements as determined by the investigator

4.5 Study Objective

4.5.1 Primary Objectives

Primary Objective

To evaluate the total amount of clinical time as defined by number and duration of visits in a new model (Group A) compared to a traditional clinical care schedule (Group B).

Secondary Objectives

1. To compare speech perception in quiet as measured on CNC words in the implanted ear.
2. To compare subject hearing outcome satisfaction on the SSQ-12 between the two models.
3. To compare device and accessory use of subjects as measured by a device use questionnaire and datalogging between the two models.
4. To compare clinician satisfaction between the models through a questionnaire.
5. To compare speech perception in noise as measured on AzBio +10 S/N in their everyday listening situation using the subjects preferred noise program and accessory if appropriate.

5. Investigational Procedures

5.1 Subject Identification

All individuals who provide informed consent (sign the informed consent form) are considered enrolled into the study and will be assigned a unique identifier. A unique alphanumeric code will identify each subject throughout the course of the study. For example, US01-SOC-0000, where:

- US = United States,

- 01 = a sequential numeral corresponding the order in which a subject is enrolled into the study for a given study site, in this case this would correspond to the first subject recruited into the study for a particular site,
- SOC=an abbreviation for the study,
- 0000 = a unique, numeric study site identification.

5.2 Release of Medical Information

Subjects will be required to release the exchange of medical information between the Investigator(s) and the Sponsor. This requirement will be clearly identified in the Informed Consent form.

5.3 Description of Study Measures

5.3.1 Patient Outcome Measures

Psychophysical Tests

This term is an overarching name for the following tests: Speech audiometry, phoneme discrimination, loudness scaling, and audiometry. All tests are completed via a direct connect system and collect data regarding detection, discrimination and identification of sound through the cochlear implant. Results from these tests are incorporated into recommendations for the AI MAP. Specific tests within the psychoacoustic test battery to be completed at each study visit are based on recommendations through the AI.

The following psychoacoustic tests will be completed through a direct connect system for the new model group (Group A):

- Speech audiometry

For this study, 25 CNC words randomly selected from each list will be administered in quiet at each level equal to 40, 55, 70 and 85dB SPL for speech audiometry. Testing will be completed and scored as the percentage of correctly repeated phonemes. An average phoneme score will be calculated within the test module, across the four presentation levels.

- Phoneme discrimination

The phoneme discrimination test is performed using up to 20 pre-defined speech sound contrasting pairs (a-r, u-ʃ, u-a, u-i, i-a, o-a, i-e, m-z, s-ʃ, e-a, u-o, ə-a, ə-o, ə-e, ə-i, z-s, v-z, ə-u, u-y, y-i). Phoneme pairs have been

established as linguistically representative and are tested at 70 dB HL in an oddity paradigm (Govaerts et al., 2006). Subjects will provide a behavioral response (e.g., hand raise or verbal response) if a discrimination is recorded for the phoneme contrast. Two correct responses are required to be considered as correct identification as scored by the Investigator. Training for at least one phoneme pair will be completed for each study visit to ensure familiarity with the test.

- Loudness scaling

Loudness scaling testing is completed by presentation of one-third octave narrow band noises centered at 250, 1000, and 4000 Hz. A 1876 ms duration stimulus will be presented randomly twice at 5dB increments between 30 and 80dB HL. Loudness will be scored on a visual analogue scale ranging from 0 (inaudible) to 6 (too loud) by the subject. (Varenburg et al. 2011, Govaerts et al, 2006, Hereen et al., 2012).

- Audiometry

Aided audiometric thresholds will be obtained using narrow band noise and the standard audiometric technique at the following frequencies 250, 500, 1000, 2000, 3000, 4000, 6000, Hz.

In addition, one list of AzBio +10 S/N at S0N0 in the sound field in the two-ear listening condition using the subjects preferred noise program and accessory if appropriate will be completed in a calibrated sound booth.

Two lists of CNC words of 50 monosyllabic words in CD format will be administered in quiet at a level equal to 60dBA in the soundfield and scored as total number of words correct, which will be expressed as a percentage correct for this study. Subjects will be tested in the unilateral condition using a configuration of speech at 0° azimuth in quiet in a calibrated sound booth.

The following speech perception tests will be administered to the traditional model group (Group B):

- One list of AzBio +10 S/N at S0N0 in the sound field in the two-ear listening condition using the subjects preferred noise program.
- Two lists of CNC words of 50 monosyllabic words in CD format will be administered in quiet at a level equal to 60dBA in the soundfield and scored as total number of words correct, which will be expressed as a percentage

correct for this study. Subjects will be tested in the unilateral condition using a configuration of speech at 0° azimuth in quiet in a calibrated sound booth.

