Study Overview	
The clinical investigation is evaluating a new clinical model in a group of newly implanted subjects who have already been consented to CI surgery.
 
This randomized multi-center study will investigate a new model (Group A) based on outcome evidence, a standardized programming and testing method that utilizes artificial intelligence and will be compared to a traditional clinical model (Group B).

Primary Objective	To evaluate the total amount of clinical time as defined by number and duration of visits in a new model (Group A) compared to a traditional clinical care schedule (Group B)
Secondary Objectives	
 1. To compare speech perception in quiet as measured on CNC words in the implanted ear. 2. To compare subject hearing outcome satisfaction on the SSQ-12 between the two models. 3. To compare device and accessory use of subjects as measured by a device use questionnaire and datalogging between the two models. 4. To compare clinician satisfaction between the models through a questionnaire. 5. To compare speech perception in noise as measured on AzBio +10 S/N in their everyday listening situation using

	the subjects preferred noise program and accessory if appropriate.
Primary Endpoint	Reduction in the overall number of minutes of cochlear implant appointments over the first 6 months post activation in the new model (Group A) compared to the traditional model (Group B).
Secondary Endpoints	
 1. Speech perception on CNC at 3 and 6 months post activation will be the same or better in the new model group compared to the traditional model. 2. Subjective hearing outcome satisfaction on the SSQ-12 at 6 months post activation will be the same or better in the new model group compared to the traditional model. 3. Device and accessory use will be the same or better at 6 months of device use with the new model compared to the traditional model as measured by a device use questionnaire and datalogging. 4. Clinician satisfaction will be the same or better with the new model when compared to the traditional model at the 6-month interval. 5. Speech perception on Az-Bio +10 S/N at 6 months post activation in the subjects everyday listening condition will be better than the pre-operative score.

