5.5.4 Three Month Post activation

At 3 months post activation, the following procedures will be completed:

- New Model (Group A)
 - Confirm Device use through usage data screen in Custom Sound
 - Administer psychoacoustic tests to include:
 - Any pending outcomes requests from 1-month visit
 - Loudness scaling
 - Speech Audiometry
 - Obtain FOX (AI) advice
 - Review CNC performance at 70dB on speech audiometry to determine if recipient tracking to ≥ 20 pre-post improvement on CNC words
 - If meets above criteria and AI has no other recommendations (Green/Teal FOX): Provide AI MAP for take home use. If recommendations have been made, complete at 6 month visit

as part of Pending Outcomes. Provide the MAP with the best outcome for take home use.

- If **not** completed at 1 month, provide appropriate accessory materials for self-driven learning based on goals of COSI.
- If does **not** meet above criteria (≥ 20 CNC words) and/or AI has made modifications to the fitting and wants additional outcome measures, complete as requested.
 - Obtain FOX (AI) advice to see if the outcome has improved. Provide the MAP with the best outcome for take home use.
 - If **not** completed at 1 month, provide appropriate accessory materials for self-driven learning based on goals of COSI
 - Complete Clinician reported Materials/Tools questionnaire
 - Communication Documentation form
 - Update COSI (Degree of Change)
 - An anonymized .cdx file will be provided to the study sponsor
 - CNC Words: Two lists of 50 monosyllabic words at 60 dBA in the soundfield using a configuration of speech at 0° azimuth in quiet for the implanted ear (contralateral ear plugged)
- Traditional Model (Group B)
 - Programming and/or counselling as defined by Center
 - Communication documentation form
 - Update COSI (Degree of Change)
 - CNC Words: Two lists of 50 monosyllabic words at 60 dBA in the soundfield using a configuration of speech at 0° azimuth in quiet for the implanted ear (contralateral ear plugged)
 - An anonymized. cdx file will be provided to the study sponsor

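### At 3 and 6 months only Group A must hear 100 CNC words in speech audiometry, and the protocol neither separates those words from the CNC endpoint lists nor fixes the test order

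*Protocol*

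**What the plan says.** Section 5.3.1 gives Group A a direct-connect test battery. Its speech audiometry uses CNC material: "25 CNC words randomly selected from each list will be administered in quiet at each level equal to 40, 55, 70 and 85dB SPL". Results are scored by phoneme and feed the AI's fitting advice.

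Sections 5.5.4 and 5.5.5 name speech audiometry for Group A at 3 and 6 months. The clinician then acts on it; at 3 months the instruction is: "Review CNC performance at 70dB on speech audiometry to determine if recipient tracking to ≥ 20 pre-post improvement on CNC words". If the criterion is missed or the AI has changed the fitting and wants more measures, those are carried out, followed by "Obtain FOX (AI) advice to see if the outcome has improved" and "Provide the MAP with the best outcome for take home use". The 6-month text has a similar branch for further measures.

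Lower in the same visit lists comes the endpoint test, "CNC Words: Two lists of 50 monosyllabic words at 60 dBA in the soundfield", for the implanted ear. Section 5.3.1 describes this test alike for both arms, word-scored and presented from CD. The only speech tests it lists for Group B are AzBio and the two CNC lists. Group B's 3- and 6-month lists begin with programming or counselling as the centre defines it, and the CNC test follows.

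The synopsis makes "Speech perception on CNC at 3 and 6 months post activation" the first secondary endpoint, with Group A expected to do at least as well as Group B. Section 10.1 adds counts, in each group, of subjects gaining at least 20% at 3 months and at least 30% at 6 months.

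**The concern.** Both arms sit the same endpoint test, but at the same visit one arm is also required to repeat back 100 words of the same test type, selected at random from the lists. No sentence reserves lists for the endpoint, removes them from the audiometry pool, or says which test comes first. A site that works down the page will test Group A after that exposure and Group B without it.

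Two effects could follow, in opposite directions. Having heard some of the words, or having practised the task, could raise Group A's score. A longer test session could lower it. Neither says anything about the quality of the care model.

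The CNC endpoint is the main objective evidence that less clinic time does not cost hearing performance. A claim of being at least as good is helped by any upward artefact in the new-model arm, and the section 10.1 counts use the same scores. Baseline adjustment would not remove the effect, because section 5.4.3 lists no speech audiometry before surgery in either arm.

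**Working it through.** The protocol gives no figure for this point, so there is nothing to reproduce. The check is a count, a comparison of the visit lists, and two conditional calculations.

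**1. Words per visit.** Inputs from section 5.3.1.
- Speech audiometry: 25 words × 4 levels = 100.
- Endpoint test: 2 lists × 50 words = 100.

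**2. The arms side by side at 3 and 6 months** (sections 5.3.1, 5.5.4, 5.5.5).

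| Item | Group A | Group B |
|---|---|---|
| Required CNC words apart from the endpoint test | 100, more if speech audiometry is repeated | 0 |
| Place in the list | before the endpoint test | not applicable |
| Programming possible at the visit | yes, on AI advice | yes, as the centre defines |
| Place of programming in the list | before the endpoint test | before the endpoint test |
| MAP worn for the endpoint test | not stated | not stated |
| Endpoint lists kept separate | not stated | not applicable |
| Order of procedures | not stated | not stated |

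The difference between arms lies in the first two rows. Programming and the unstated MAP apply to both.

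**3. Cumulative exposure if the listed order is followed.** By the 6-month endpoint test: 100 + 100 = 200 required speech-audiometry words in Group A against 0 in Group B. If the AI asked for one full repeat of speech audiometry, the count at that visit would be 2 × 100 = 200.

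**4. Possible overlap with the endpoint words.** Assumptions: the audiometry and endpoint words come from one pool of P distinct words, and the 100 audiometry words are drawn at random without regard to the endpoint lists. The protocol does not give P. Expected number of endpoint words already heard that day = 100 × 100 / P.

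| Assumed P | Endpoint words already heard |
|---|---|
| 200 | 50 |
| 300 | 33 |
| 500 | 20 |
| 1000 | 10 |

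If the two sets share no words, the overlap is 0. With one full, independently drawn repeat the share is 1 − (1 − p)², where p is the single-run share: 75% for P = 200 (p = 0.5) and 36% for P = 500 (p = 0.2).

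**5. What a shift would mean at this sample size.** The total is 35 to 50 (synopsis). Assume equal arms of about 17 to 25 and a standard deviation of 15 to 25 points; the protocol states neither. The standard error of the arm difference is SD × √(2/n):
- smallest: 15 × √(2/25) = 4.2 points
- largest: 25 × √(2/17) = 8.6 points

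A net shift of 2 points would then be 2/8.6 = 0.23 to 2/4.2 = 0.47 standard errors; a shift of 5 points, 0.58 to 1.18. These are reference shifts only. No step leads from the overlap in step 4 to a gain in score.

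**The case against.** **The order is only bullet order.** The lists say what is to be completed, not in what sequence, and they do not read as strictly chronological: at 3 months the export of the session file stands before the CNC test in Group A and after it in Group B. This is right, so it cannot be said that the protocol requires the endpoint test to come second. But it allows that order and lists it that way.

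**Speech audiometry might not be given every time.** Section 5.3.1 says "Specific tests within the psychoacoustic test battery to be completed at each study visit are based on recommendations through the AI". Against that, 5.5.4 and 5.5.5 name speech audiometry outright and base a clinician's review on it. A repeat is a different matter: the further measures could be any test in the battery, so counts above 100 are conditional.

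**Group B may also hear CNC words.** Section 4 says that the traditional model includes outcome testing in a sound booth, with content left to the clinic. Zero is therefore what the protocol requires of Group B, not a guarantee of what happens. Unregulated testing there would not make the arms alike.

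**Hearing a word once may help little.** A quarter of the audiometry words are presented at 40 dB SPL and may be poorly heard. No feedback to the subject is described, and scoring and presentation differ from the endpoint test. This stands, and is why no gain in points is claimed.

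**A reader might infer that only Group A can be tested on a newly changed MAP.** The documents do not support that. Group B may be programmed at the same visits, also listed ahead of its CNC test. How the MAP is changed differs, but that is part of the care models under comparison. The Group A text says which MAP goes home, not which is worn for the test.

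**Conclusion.** The concern holds in a limited form. At 3 and 6 months Group A has a required 100 CNC words that Group B does not, listed ahead of the endpoint test, with no separation of word lists and no stated order. The first secondary endpoint and the 20% and 30% counts can therefore be affected by unequal same-day exposure and test load.

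The firm figures are 100 against 0 required words per visit and, if the listed order is followed, 200 against 0 by the 6-month endpoint test. The overlap of about 10 to 50 words in 100 rests on an assumed common pool of 1000 to 200 words and could be nil. A reader might infer a bias of known size in favour of Group A. The protocol supports neither a size nor a direction, since exposure and fatigue pull opposite ways and no gain per word heard is given.

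The unstated MAP is a gap in both arms, not a one-sided bias. The primary endpoint, appointment minutes, does not rest on CNC scores. The point is worth correcting because the remedy is cheap and the endpoint is meant to show that hearing is not compromised.

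**What to change.** In sections 5.5.4 and 5.5.5:

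1. State that the soundfield CNC test is done before any speech audiometry at that visit, and at the same position in the visit in both arms.
2. Reserve the CNC lists used for the endpoint and exclude them from the words available to speech audiometry. Testing first removes same-day exposure; reserving the lists also covers carry-over from the 3-month visit to the 6-month visit.
3. State one rule, identical in both arms, for which MAP is worn during the endpoint test. Which MAP that is remains the sponsor's choice.

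The cost is a few sentences, a list-allocation table, and slightly less scheduling freedom at two visits. The argument here concerns CNC words, so it gives no reason to move AzBio.

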5.3.1.1 Clinician Based Survey

This questionnaire developed by Cochlear focuses on the current clinical model and practices that are clinic centric and variable.

5.3.1.2 Speech, Spatial, Qualities (SSQ-12)

The SSQ-12 (Gatehouse & Noble, 2013) will be used as a subject self-assessment in three categories (speech hearing rating scale, spatial rating scale, and sound qualities rating scale) for both Group A and B.

5.3.1.3 Client Oriented Scale of Improvement (COSI)

The COSI™, developed by the National Acoustic Laboratories, is a subjective outcome measure completed by the audiologist with input from the patient across 2 appointments. However, can be repeated as the patient gets more experience with their device and continues to improve in their listening abilities. At the first appointment the patient should identify specific situations where they currently struggle and would like to see improvement with an implantable hearing solution. After the implantable hearing solution has been fit, the recipient is asked to record the change in hearing function in those same situations. The five choices of response vary from “worse” to “much better.” The patient is also asked to report their final hearing ability from “hardly ever” to “almost always.” Some patients may prefer to describe their improvement and hearing abilities. This will be completed for Group B as part of the new model.

5.3.1.4 Unscheduled Visit Form

If the subject requires an interim clinical visit for programming, counselling, troubleshooting or any other clinical reason, an Unscheduled Visit Form will be completed (Group A and B). Information collected will include the date of the visit, reason for the visit, and activities completed.

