Study Inclusion Criteria	
 • Patients who are receiving a commercially approved Nucleus® electrode • 18 years and older • Postlingual onset of hearing loss (onset of hearing loss >two years of age) • Individuals who qualify for cochlear implantation using the clinics current CI candidacy criteria • Individuals who have recently been implanted but not yet had their external device activated

	
 • Willingness to participate in a study and comply with all study requirements • Fluent in spoken English
Study Exclusion Criteria	
 • Ossification or any other cochlear anomaly that might prevent insertion of less than 10 electrodes of the electrode array • Diagnosis of retro-cochlear pathology • Diagnosis of auditory neuropathy • Subject considering an acoustic component in the implanted ear • Unrealistic expectations on the part of the subject regarding the possible benefits, risks, and limitations that are inherent to the surgical procedure and use of the prosthetic device • Unwillingness or inability to comply with all investigational requirements • Severe-profound sensorineural hearing loss >30 years • Previous cochlear implant in the contralateral ear. 
Additional cognitive, medical or social handicaps that would prevent completion of all study requirements as determined by the investigator

Study Intervals	
New Model (Group A): Pre-operative, switch-on, 1-month, 3 month and 6 months
 
Traditional Model (Group B): Pre-operative, switch-on, 1-month, 3 month and 6 months with time measurements for any additional visits included within their typical clinical care schedule.

2. Glossary

Term	Definition
CI	Cochlear Implant
IA	Initial Activation
AE	Adverse Event
IRB	Institutional Review Board
CRF	Case Report Form
SAE	Serious Adverse Event
Direct Connect	Subject evaluation including the Personal Audio Cable or mini-mic outside of the soundfield. Also referred to in separate documents as CoalaLink.
MAP	Individualized listening program created for cochlear implant recipients
AI	Artificial Intelligence: behaves similar to car navigation. Logic based in knowledge, decision making and learning capacity.
Artificial Intelligence (AI) MAP	Map created with AI

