Based on data collected through survey's, focus groups and clinical observations, there is no standardized approach to the number of clinical visits, programming methodology or tools and materials used in the aftercare treatment of the Adult CI recipient (Dunn 2018, Global Audiology Focus Group 2018). Patients are typically seen 7-10 times in the first-year post CI surgery regardless of their performance. Changes to the recipient's MAP, usually T and C levels, are typically based only on subjective feedback from the recipient and not based on data. This may be due to several reasons including: inconsistent collection of outcome data due to limited sound booth access, lack of benchmark milestones for performance, uncertainty of what parameters to change based on the data they have obtained or clinician preference. This has resulted in a complex and inefficient delivery model. It is unclear the impact this has on the variability seen in patient outcome and hearing satisfaction. In summary there is no standardization to the traditional model and the model can therefore vary from clinic to clinic.

A standardized evidence based adult delivery model has been created using clinical and recipient milestones, clinical outcomes, an AI based programming tool, standardized test paradigm and defined materials and tools to help guide the professional through the clinical aftercare process.

The clinician milestones were created using global data which includes impedance stabilization within the first 60 days, T and C levels by 3 months and data from the Nucleus® CI532 Cochlear Implant in Adults study which suggests pre-post CNC performance for 80% of the study group was $\geq 20\%$ at 3 months and $\geq 30\%$ at 6 months (M. Bewley, Mining clinical databases: Post-Hoc study 2013; Nucleus CI532 Cochlear Implant in Adults study, Preliminary data 2018) .

A clinical decision support tool using AI and evidence (performance tests) collected through a direct connect system is also used in the model. The recommendations by the AI agent is outcome driven based on data from psychoacoustic tests (Bermejo et al, 2013, Varenberg et al 2011, Govaerts et al 2010). The

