The clinical investigation is evaluating a new clinical process in a group of newly implanted subjects.

The new model (Group A) that uses a prescriptive method to deliver CI care in newly implanted adults will be compared to a control method defined as the clinics existing or (Group B) traditional model (i.e. programming, outcome testing completed in a sound booth and materials used for device counseling). The new clinical process standardizes the care model through clinical outcomes, AI based programming, test battery completed through direct connect and tools and materials used for counselling. The goal is to reduce the total amount of clinical time as defined by number and duration of visits compared to the clinics traditional model without compromising clinical outcomes or patient satisfaction.

Group A Study participants will be evaluated during the switch on ,1-month, 3-month and 6-month post op visit. In addition, sound processor and accessory usage data will be collected as well as psychophysical tests completed as part of the clinical decision support tool. Outcome measures will be collected at 3 and 6 months post activation. Total time of the appointment will be collected for each visit using a timer. Programming will be calculated from the CDX file which includes a time stamp. Other activities (accessories, device use, counseling etc.) will be estimated based on subtracting programming time from the total time of the sessions.

- Total time of appointment:
 - Timer will be started when the professional and subject are seated in the consultation room to end the session.
- Programming time
 - Will be extracted from the CDX file based on the time stamps within the session file.

- Other activities (accessories, device use, counseling etc.)
 - Will be estimated based on subtracting programming time from the total time of the sessions.
 - Note: Data entry or forms associated with data collection are not included in the total time of the appointment

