Group B subjects will be evaluated at each clinic visit as part of the clinics traditional model on sound processor and accessory usage data. The same three-time measurements will be collected for each visit as Group A. Outcome measures will be collected at 3 and 6 months post activation. Total time of the appointment will be collected for each visit using a timer. Programming will be calculated from the CDX file which includes a time stamp. Other activities (accessories, device use, counseling etc.) will be estimated based on subtracting programming time from the total time of the sessions.

- Total time of appointment:
 - Timer will be started when the professional and subject are seated in the consultation room to end the session.
- Programming time
 - Will be extracted from the CDX file based on the time stamps within the session file.
- Other activities (accessories, device use, counseling etc.)
 - Will be estimated based on subtracting programming time from the total time of the sessions.
 - Note: Data entry or forms associated with data collection are not included in the total time of the appointment

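### The protocol says every visit is timed, but its text on unscheduled visits provides no place to record their minutes, which belong in the primary endpoint

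*Protocol*

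**What the plan says.** The synopsis defines the primary endpoint as "Reduction in the overall number of minutes of cochlear implant appointments over the first 6 months post activation", Group A against Group B. Nothing limits it to scheduled appointments.

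Section 4 gives the measurement rule. For Group A: "Total time of the appointment will be collected for each visit using a timer". The same sentence appears for Group B, together with "The same three-time measurements will be collected for each visit as Group A". The Group A paragraph opens with a list of visits: "Group A Study participants will be evaluated during the switch on ,1-month, 3-month and 6-month post op visit". Programming time has its own source: "Will be extracted from the CDX file based on the time stamps within the session file".

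Unscheduled visits are handled elsewhere. Section 5.3.1.4 requires an Unscheduled Visit Form in both groups for any interim clinical visit, and describes its content: "Information collected will include the date of the visit, reason for the visit, and activities completed". Section 7 directs sites to document unscheduled visits on that form. The Time measurement rows of Tables 1 and 2 mark scheduled visits only.

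Under Study Intervals, the synopsis gives Group B its scheduled visits "with time measurements for any additional visits included within their typical clinical care schedule". The Group A entry lists scheduled visits and has no matching clause. Section 10.1 plans to compare the number of and reasons for unscheduled visits, which it describes as lying outside both models. It does not mention their minutes.

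**The concern.** An interim visit for reprogramming or troubleshooting is a cochlear implant appointment, so its minutes belong in the endpoint. The section 4 rule, read literally, includes it. But a site working from the form description and the visit tables finds no place to put the time, and a CRF built to those two places would not collect it.

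This is a data-capture problem. How minutes are summed can be left to the SAP, but minutes that were never timed cannot be recovered at analysis. The CDX time stamps give programming time, not total appointment time, and section 5.5 asks for the .cdx file only at scheduled visits. Counselling and troubleshooting minutes at an untimed visit would be lost.

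A loss that is equal in both arms does not move the difference in minutes. Bias arises if unscheduled visits are more frequent in one arm, or if they are timed in one arm and not in the other. The second route has some basis in the text. The synopsis tells sites to time extra typical-care visits in Group B, and section 3 says of typical care: "In summary there is no standardization to the traditional model and the model can therefore vary from clinic to clinic". A similar interim visit could be timed as typical care in Group B and only logged on the form in Group A.

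**Working it through.** The protocol has no figure to reproduce: it gives no unscheduled-visit rate and no visit length. The check has two parts.

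**1. The text, side by side**

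| Place in protocol | Scheduled visits | Unscheduled visits |
|---|---|---|
| Section 4, timer rule | Timed | Covered by the literal wording, not named |
| Synopsis, Study Intervals | Listed for both groups | Timing of additional visits stated for Group B only, and only within typical care |
| Section 5.3.1.4, form | Not applicable | Date, reason, activities; no duration |
| Tables 1 and 2, Time measurement | Marked | No column |
| Section 5.5, .cdx file | Requested | Not mentioned |
| Section 10.1 | – | Number and reason; no minutes |

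The table row is a weak sign taken alone. Tables 1 and 2 have no unscheduled column for any measure, and the synopsis shows that they do not list every timed visit. The form content and the one-sided synopsis clause carry more weight.

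**2. Sensitivity, on assumed values**

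From the protocol: four timed scheduled visits in Group A (switch-on and 1, 3 and 6 months), five in Group B (the same plus 1–2 weeks), and five sites, the stated maximum. Assumed: scheduled visits of equal length, equal enrolment per site, and the following quantities:

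- dA, dB: unscheduled visits per subject in each arm
- w: length of an unscheduled visit relative to a scheduled one
- fA, fB: share of sites not timing unscheduled visits in each arm

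Recorded A = 4 + (1 − fA)·dA·w

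Recorded B = 5 + (1 − fB)·dB·w

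Recorded reduction = (B − A)/B

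The true value has fA = fB = 0. One site of five not timing is f = 0.2; no site timing is f = 1.

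| Scenario | True | f = 0.2 | f = 1 |
|---|---|---|---|
| dA = 0.5, dB = 0, w = 1 | (5 − 4.5)/5 = 10% | (5 − 4.4)/5 = 12% | (5 − 4)/5 = 20% |
| Same, w = 0.5 | (5 − 4.25)/5 = 15% | (5 − 4.2)/5 = 16% | 20% |
| dA = dB = 0.5, w = 1, same practice in both arms | 1/5.5 = 18.2% | 1/5.4 = 18.5% | 1/5 = 20% |
| dA = dB = 0.5, w = 1, Group B always timed (fB = 0; f is fA) | 18.2% | (5.5 − 4.4)/5.5 = 20.0% | (5.5 − 4)/5.5 = 27.3% |
| dA = 0, dB = 0.5, w = 1 | (5.5 − 4)/5.5 = 27.3% | (5.4 − 4)/5.4 = 25.9% | (5 − 4)/5 = 20% |

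In the third row the absolute difference stays at one visit, and only the percentage changes because its denominator shrinks. In the last row the error runs against the new model. If Group B had one further timed typical-care visit in the first scenario (B = 6), the values would be 1.5/6 = 25.0%, 1.6/6 = 26.7% and 2/6 = 33.3%.

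**The case against.** The strongest reply is that the rule already exists and is unqualified. Section 4 times each visit in both arms, the endpoint says overall minutes, and no sentence excludes unscheduled visits. On this reading section 5.3.1.4 merely omits to repeat a rule set elsewhere. Its list is introduced by wording that need not be exhaustive, and completing the form does not prevent running the timer. The Group B clause in the synopsis may exist only because Group B's routine schedule varies by clinic while Group A's is fixed. Section 10.1 may simply supplement an endpoint that already counts these minutes. CRF instructions are separate documents (section 12.5) and may include a duration field. Finally, the large shifts in the table require every site to disregard section 4. With one site doing so, the shifts are about 0.3 to 2 percentage points.

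Much of this stands. There is no flat contradiction, a loss of minutes is not demonstrated, and the percentages show sensitivity only. But duration is the primary endpoint variable, and it is the item missing from the description of the one form used for these visits. A general rule that the form description and the tables do not carry through, and that the synopsis extends explicitly to additional visits in one arm only, invites uneven practice. If the CRF already has the field, aligning the protocol costs a sentence.

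**Conclusion.** The concern holds as a gap in data capture: the protocol's operational text does not implement its own timer rule for unscheduled visits, so minutes of the primary endpoint could be lost, possibly differently by site or arm. It should be fixed; confidence is medium.

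Neither the direction nor the size of any bias can be determined from the protocol. On the assumed values, the error in the percentage reduction runs from a fraction of a point (equal rates and practice, one site not timing) to about 9 to 10 points (no site timing Group A's unscheduled visits, with Group B having none or having all of its own timed). It understates the reduction if the excess visits are in Group B. The conclusion rests on the protocol text alone; the SAP and the CRF instructions were not available, and the CRF could already close the gap.

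**What to change.** - Add total appointment minutes, with timer start and stop, to the Unscheduled Visit Form in section 5.3.1.4 for both groups.
- Add unscheduled visits to the Time measurement rows of Tables 1 and 2.
- State in the primary endpoint that minutes are summed over all scheduled and unscheduled cochlear implant appointments from switch-on through the 6-month visit, in both arms.

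The cost is one field on an existing form, one table entry per group and one sentence. The measured reduction may turn out less favourable to the new model once these minutes are counted.
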